Appendix A: InterGraft™ Venous Anastomotic Connector Instructions for Use

Appendix B: Sample Informed Consent Form

Appendix C: Case Report Form

ACRONYMS AND ABBREVIATIONS

AE	Adverse Event
AIG	Arterial InterGraft Connector
AV	Arteriovenous
AVG	Arteriovenous graft
CEC	Clinical Events Committee
CRF	Case Report Form
DCC	Data Coordination Center
EDC	Electronic Data Capture
GCP	Good Clinical Practice
IFU	Instructions for Use
IRB	Institutional Review Board
KDOQI	Kidney Disease Outcomes Quality Initiative (National Kidney Foundation)
ePTFE	expanded Polytetrafluoroethylene
UADE	Unanticipated Adverse Device Effect
VIG	Venous InterGraft Connector
VIG-CAS	Venous InterGraft Continued Access Study

1.0 GENERAL INFORMATION

Study Name: Continued Access Study of the InterGraft™ Venous Anastomotic Connector for Minimally Invasive Connection of an Arteriovenous Graft for Hemodialysis

Study Device: InterGraft™ Venous Anastomotic Connector

Study Device

Regulatory Status: Investigational Device. Limited by Federal (United States) law to investigational use.

**Indication for Use:
(proposed)**

The InterGraft™ Venous Anastomotic Connector provides a minimally invasive, sutureless method for attachment of an arteriovenous graft to a vein in the upper extremity. The InterGraft™ Venous Anastomotic Connector facilitates creation of the arteriovenous graft connection to a vein in support of hemodialysis in subjects with End Stage Renal Disease. The InterGraft™ Venous Anastomotic Connector is used together with conventional suturing of the arterial anastomosis to facilitate creation of an arteriovenous graft in support of hemodialysis in subjects with end stage renal disease.

Study Design: Prospective, multicenter, non-randomized study

Subjects: Up to 15 subjects with end stage renal disease who have a planned arteriovenous graft implant procedure for hemodialysis access and who meet the study selection criteria will be included.

Sponsor: Phraxis, Inc.
Saint Paul, MN
Sponsor representative: [name]., Director of Clinical Affairs
[contact]

**Data Coordination &
Statistical Analysis** Technical Resources International, Inc.
Bethesda, MD
Project Manager: [name]
[contact]

Clinical Events

Committee (Chair): [name]
Neptune, NJ
[contact]

2.0 INTRODUCTION AND BACKGROUND

The traditional sutured graft-to-vein anastomosis suffers from stenosis that subsequently develops due to neointimal hyperplasia. This pathology is thought to form due to surgical implant trauma to the vein and surrounding tissues, the sutures themselves, as well as turbulent flow across the anastomosis. The novel InterGraft™ Venous Anastomotic Connector (VIG) is designed to provide a minimally invasive anastomosis for arteriovenous (AVG) implantation that may avoid the pathology and clinical problems currently associated with a sutured anastomosis.

The recently completed ‘VIG-only’ pivotal study evaluated the safety and effectiveness of using the VIG for the venous anastomosis, together with traditional suturing of the arterial anastomosis for implantation of an AVG for hemodialysis. The VIG-only study was approved by FDA (IDE G140221) and included 158 subjects contributed from 10 USA study sites. Collected data included baseline characteristics, AVG patency and use for hemodialysis, AVG interventions, and adverse events throughout a six-month follow-up period. The primary study endpoint was cumulative graft patency at 6 months. Secondary endpoints included evaluation of primary unassisted patency at six months, the number and type of AVG interventions, and serious adverse events including rates of death, AVG infection, emergent surgery, significant bleeding and pseudoaneurysm.

Results of the VIG-only study showed that the primary endpoint of cumulative graft patency at 6 months, assessed by comparison to a target Performance Goal of 75%, was met (P-value < .001). By Kaplan Meier survival analysis, the lower 95% Confidence Bound for cumulative patency at 180 days was 86.98%. Primary unassisted patency was 60.21%, with a lower 95% Confidence Bound at 180 days of 50.84%. There were four deaths (2.5%), none of which were related to the VIG study device. Six subjects had AVG infections (3.8%) resulting in surgical excision of the graft. None of the AVG infections were related to the VIG study device. There were no reports of emergent surgery, significant bleeding or pseudoaneurysm. These results provide evidence of VIG efficacy for creating a venous anastomosis during AVG implantation, with no significant safety concerns.

Phraxis, Inc. (Sponsor) is currently preparing an application to FDA for marketing clearance of the VIG. The continued access study of the VIG (hereafter referred to as the ‘Venous InterGraft Continued Access Study, or ‘VIG-CAS’) described in this investigational plan allows for continued enrollment of subjects while the marketing application is being prepared and subsequently reviewed by FDA. The VIG-CAS will include the same patient population, follow-up schedule, and study endpoints as the VIG-only study.

The VIG-CAS will be conducted in compliance with the Investigational Plan, Investigational Device Exemption (IDE) regulations, Good Clinical Practice guidelines (GCP), and other applicable regulatory requirements.

3.0 STUDY DEVICE DESCRIPTION

The VIG is designed for transcatheter delivery within a 4 -7 mm diameter peripheral vein, and connection to an 6 mm AVG that has been tunneled under the skin in a standard manner. The connection is made via a small skin incision. The VIG is constructed as a nitinol framework encapsulated with ePTFE in the midsection and uncoated at the ends (**Figure 1**). The VIG distal flared end is configured as a nitinol scaffold with anchoring barbs that extend into the vein wall, and the proximal ‘graft end’ is a stent-like framework for anchoring within the AVG.

The VIG is intended as a permanent implant. The VIG is delivered and deployed within the target vein using a customized transcatheter delivery system. A detailed description of the VIG and delivery system is provided in the Instructions for Use (**Appendix A**).

Figure 1- InterGraft Venous Anastomotic Connector (VIG). Note barbs that anchor VIG within the vein (arrow).

Indication for Use (proposed)

The InterGraft™ Venous Anastomotic Connector provides a minimally invasive, sutureless method for attachment of an arteriovenous graft to a vein in the upper extremity. The InterGraft™ Venous Anastomotic Connector facilitates creation of the arteriovenous graft connection to a vein in support of hemodialysis in patients with End Stage Renal Disease. The InterGraft™ Venous Anastomotic Connector is intended to be used together with conventional suturing of the arterial anastomosis to facilitate creation of an arteriovenous graft in support of hemodialysis in patients with End Stage Renal Disease.

4.0 PRIOR STUDIES

The VIG, together with an arterial InterGraft Connector (AIG), were evaluated in prior studies as summarized below. The findings from the prior studies are also applicable to use of the VIG only.

NOTE: The AIG has been discontinued and it is not studied in this investigational plan.

Bench Testing

Bench testing of the VIG confirmed the structural integrity of the device, adequacy of resistance to compressive forces and radial forces, adequacy of bond strengths, kink and migration resistance, and verification of critical dimensions. Where applicable, testing was conducted using commercial 6mm ePTFE grafts that were selected due to their current widespread clinical use.

Pre-Clinical Studies

Simulated use testing was performed for verification of the VIG deployment procedure. The VIG performed adequately for intended use with respect to the ability to access, deploy and withdraw.

Acute animal studies evaluated the deliverability of the VIG, the ability to complete an AV circuit using ePTFE grafts, and near-term graft patency following initial implantation of grafts using a VIG and AIG.¹ Testing was

performed using a canine femoral artery/vein model. These studies provided evidence of safety and acceptable performance of the VIG and AIG.

Clinical Studies

First-in-Human Study

A first-in-human clinical evaluation of the VIG and AIG was performed.² The study was conducted at the Italian Hospital in Asuncion, Paraguay, under a protocol that was approved by the Paraguayan National Regulatory Authority and the institutional Ethics Committee. All subjects provided prior written consent, and the study was conducted in accordance with ICH Guideline for Good Clinical Practice. The InterGraft connectors were successfully used in 9/9 subjects for connection of an AVG in the upper arm: five subjects received both the VIG and the AIG, and four subjects received the VIG for the venous anastomosis and a standard sutured arterial anastomosis. Delivery and deployment success was obtained in all cases. All AVGs were patent at the end of the procedure, with no procedural adverse events related to the VIG. Three subjects exited the study early for reasons unrelated to the InterGraft connectors. The remaining subjects had patent grafts at 6 months.

VIG-only Pivotal Study (IDE G140221)

As described in **Section 2.0** above, a pivotal ‘VIG-only’ clinical study was conducted under an IDE approved by FDA. The study is now completed and the primary endpoint of cumulative graft patency at 6 months with comparison to a target Performance Goal of 75% was met (P-value < .001). The results of the pivotal study provide evidence of safety and effectiveness for use of the VIG and provide justification for the continued access study described in this investigational plan.

5.0 STUDY OBJECTIVE

The objective of the VIG continued access study (VIG-CAS) is to allow study investigators and their patients continued access to the VIG while a marketing application is prepared by Phraxis, Inc. and reviewed by the FDA. The study will allow for the collection of additional safety and effectiveness data using the VIG.

6.0 STUDY DESIGN

The VIG-CAS is a multicenter, prospective, single-arm (non-randomized) study that will include up to 15 subjects contributed from up to five (5) study sites/investigators who previously participated in the VIG-only study. No new investigators will be included. All subjects will be assigned to treatment with the VIG and a standard sutured arterial anastomosis for implantation of an AVG for hemodialysis. The selection criteria (patient population), follow-up schedule, and study endpoints are the same as those used in the VIG-only study.

Study data will be collected up to the point at which each subject has completed the final 6-month follow up or experienced a terminal study event.

7.0 SUBJECT SELECTION

The following inclusion and exclusion criteria must be met for enrollment in the study:

Initial Inclusion Criteria (All must be answered YES for study eligibility.)

1. Subject is \geq 18 years of age.
2. Subject requires the creation of a vascular access graft for hemodialysis, secondary to a diagnosis of End Stage Renal Disease.
3. Subject has the vascular access graft placed in an upper extremity.
4. Baseline imaging shows suitable vascular anatomy/ vessel size for the InterGraft™ Venous Connector and an artery at least 3.5 mm in diameter that is suitable for creating the arterial anastomosis.
5. Subject has a reasonable expectation of remaining on hemodialysis for at least 6 months.
6. Subject or his/her legal guardian understands the study and is willing and able to comply with the dialysis schedule and follow-up requirements.
7. Subject or his/her legal guardian provides written informed consent. *NOTE: In accordance with the requirements of some Institutional Review Boards (IRBs), where applicable, only those subjects with capacity to consent for themselves will be included. Thus, where required by the IRB, adult individuals who lack capacity to consent for themselves will be excluded from the study.*

Final Inclusion Criterion to be applied at the time of surgery (Must be answered YES for enrollment into the study.)

8. Physician's examination at time of surgery shows no significant vessel lesions, calcification(s), anatomic structures, or abnormalities that may limit ability to safely deploy the InterGraft™ Venous Connector or create a sutured arterial anastomosis.

Exclusion Criteria (All must be answered NO for study eligibility.)

1. Subject has a documented and unsuccessfully treated ipsilateral central venous stenosis as determined by imaging.
2. Subject currently has a known or suspected bacterial, fungal, or HIV infection. *NOTE: Subjects with hepatitis B or C may be included in the study.*
3. Subject has a known hypercoagulable or bleeding disorder or requires treatment with warfarin or heparin. *NOTE: The intent of this criterion is to exclude patients with high risk for bleeding or clotting complications. Patients who are taking the oral anticoagulant Eliquis® (apixaban) may be included in the study if Eliquis is temporarily discontinued prior to the study procedure, in accordance with the approved prescribing instructions. Patients may receive anticoagulation therapy any time after the study AV graft implant procedure, at their physician's discretion. This should be driven by an indication unrelated to the vascular access.*

4. Subject has had a previous instance of Heparin Induced Thrombocytopenia type 2 (HIT-2) or has known sensitivity to heparin.
5. Subject has co-morbid conditions that may limit their ability to comply with study and follow-up requirements.
6. Subject has had >2 previous arteriovenous accesses in treatment arm.
7. Subject is currently taking Aggrenox®.
8. Subject needs or is scheduled for any major surgery within 30 days of the study procedure.
9. Subject is currently taking maintenance immunosuppressant medication such as rapamycin, mycophenolate or mycophenolic acid, prednisone (>10 mg), cyclosporine, tacrolimus, or cyclophosphamide.
10. Life expectancy is less than 12 months.
11. Subject is pregnant. *NOTE: A negative urine pregnancy test within 24 hours of the study procedure is required in all female subjects with reproductive capacity.*
12. Subject is a poor compliance risk (i.e.. history of IV or oral drug abuse).
13. Subject is enrolled in another dialysis or vascular investigational study.

8.0 STUDY ENDPOINTS

Study endpoints include the following:

Endpoint #1. Cumulative patency at 6 months, defined as the percentage of subjects free from loss of access of the AVG for hemodialysis, assessed at 6 months.

Endpoint #2. Acute device success, defined as AVG flow at the end of the procedure as determined by palpable graft thrill and/or audible bruit, without significant bleeding or emergent surgery.

Endpoint #3. Primary Unassisted Patency at 6 months, defined as the percentage of subjects free from the first occurrence of either access thrombosis or an access procedure performed to maintain access patency.

Endpoint #4. Time to First Cannulation, defined as the time from initial access placement to the first graft cannulation for hemodialysis.

Endpoint #5. Number and type of interventions required to maintain secondary patency.

Endpoint #6. Number and type of serious adverse events (SAEs) through 6 months. SAEs include the following: death, emergent surgery, AVG infection requiring treatment (e.g., prolonged or intravenous antibiotic therapy), significant bleeding (defined as bleeding requiring treatment), and pseudoaneurysm.

Expected interventions for restoration of patency will be documented and reported separately, are reflected in the evaluation of cumulative patency, and are not required to be reported/tabulated again as SAEs.

Endpoints will be evaluated acutely (at the time of implant), at time of any AVG intervention, at two weeks, and monthly through 6 months for all subjects. The study AVG patency evaluation will start immediately after the index procedure is completed (e.g., subject leaves the surgery suite). This means that once the AVG is created, patency evaluation begins. The occurrence of acute thrombus and treatment thereof during the index procedure while the vascular access is being created does not trigger the loss of primary patency.

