10.0 STUDY PROCEDURE

General Procedure

The procedure will be performed in accordance with the VIG Instructions for Use (IFU, **Appendix A**). A commercially available 6mm diameter ePTFE graft will be used. Conventional grafts or grafts designed for early cannulation (within 24-48 hours) may be used. The study procedure will be performed in an operating room that has fluoroscopic imaging capability for guiding placement of the VIG. The anesthesia regimen will be determined at the physician's discretion; there are no study-specific anesthesia requirements. A regional nerve block is typically performed for placement of an AVG. Standard, routine hemodynamic monitoring will be performed to assess cardiovascular status throughout the procedure. Heparin anticoagulation may be provided at the physician's discretion.

Small skin incisions will be made for tunneling the graft under the skin in a standard manner. The VIG device is provided pre-loaded within a customized catheter-based delivery system for over-the-wire delivery. The VIG is inserted through an introducer sheath placed in the target vein so that the 'vessel end' of the VIG is deployed within the vein, and the 'graft end' extends out of the vein for connection to the graft. Delivery and deployment will be performed under fluoroscopic guidance. The VIG will be deployed first, connected to the AVG, then the graft and VIG will be flushed and clamped. The arterial anastomosis will then be created using a standard suturing method.

NOTE: Although not expected, if connection of the venous graft segment using the VIG is attempted but not able to be completed, the venous anastomosis should be completed using standard suturing. Such situations will be considered as an acute device failure.

Following establishment of the AV circuit, the skin incisions will be sutured closed using standard techniques. The subject will be moved to a recovery area for monitoring prior to discharge. It is anticipated that most subjects will be discharged the same day or within 24 hours following the AVG implant procedure.

Use of Clamps

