Ipsilateral central venous stenosis is a study exclusion. However, a patient with central venous stenosis may be considered for the study following successful treatment of the stenosis. Central stenosis angioplasty may be performed first, then immediately followed with the study procedure. The patient may be enrolled if, as assessed by the investigator, the central stenosis has <30% residual stenosis, which is the KDOQI threshold for successful intervention. The patient should not be enrolled if the residual stenosis is $\geq 30\%$ or if the investigator determines that the treatment could impact the ability to assess the study endpoints (e.g., acute device success, graft patency, safety).

Study Device Failure, Defect, or Suspected Device Problem

Device malfunction is defined as *any occurrence in which the study device does not perform as intended, when used or attempted to be used in a study procedure*. As described in the IFU, a visual examination of the VIG should be performed at the time of opening the packaging and prior to use in a subject. Defective devices (obvious or suspected) should not be used. A replacement VIG should be obtained and the study procedure continued. A device accountability log will be used to account for all used and opened/unused devices in this study.

If a VIG defect or malfunction is discovered/suspected any time prior to vascular deployment, the VIG should not be used. A replacement device/component should be used and the study procedure continued. A Device Malfunction CRF must be completed for all device malfunctions, failures or suspected failures, and the defective product identification should be recorded on the device accountability log. Whenever possible, a defective/suspected defected VIG should be returned to the Sponsor for evaluation.

The Device Malfunction CRF should be used to report and provide details of situations in which the VIG does not perform as intended. Failure of the VIG to perform as intended may potentially be due to a variety of reasons, including defect or suspected defect in the device itself or the delivery system; operator error; anatomic issues; or other reasons. If use of the VIG is attempted but ultimately the device is not able to be used, a Device Malfunction CRF should be submitted to report the surrounding details.

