NOTE: Device Malfunctions should be reported within 24 hours of discovery. 24-hour reporting of device malfunctions will assist with Sponsor's efforts to assess whether any SAEs associated with a device malfunction may also have occurred.

Bailout Procedure

Bailout procedures are not anticipated but could potentially be required if, for example, the VIG does not deploy correctly, does not seal correctly, is not deployed at an acceptable location, or if there are any major vascular events. In such cases, the subject should be referred for surgical intervention. No attempt should be made to remove an improperly deployed VIG using percutaneous methods.

Assessment of Graft Flow at the End of the Procedure

An AVG placed using the VIG and a sutured arterial anastomosis typically has a pulse and/or thrill which is easily palpable over the skin or directly on the AVG prior to closure of the surgical incisions. Thus, the AVG flow assessment is similar that used for standard sutured AVGs. An optimal method to confirm AVG patency at the end of the implant procedure is to feel a thrill near the arterial anastomosis or confirm a Doppler signal. Auscultation using a sterile or covered stethoscope is also acceptable. At the physician's discretion and as warranted, a final angiogram may also be performed to verify patency of the graft.

Initial Use of the Graft for Hemodialysis

Initial hemodialysis cannulation of AVGs placed with the VIG should be performed in accordance with the graft manufacturer's Instructions for Use. After needle withdrawal, use gentle, non-occlusive digital pressure to compress the cannulation site until hemostasis is achieved. The VIG should NOT be directly cannulated. In accordance with standard practice, once placed, AVGs should be used for hemodialysis access as soon as deemed appropriate by the nephrologist and/or operator. For standard ePTFE AVGs, the time from placement to first cannulation is typically after two weeks. Early cannulation AVGs can be used sooner, in accordance with approved labeling. Every effort should be made to minimize infection risk by removing central catheters as soon as possible.

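### Does Endpoint #2 count a conversion to a sutured venous anastomosis as acute device success?

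*Combined protocol and SAP*

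**What the plan says.** Section 8.0 defines Endpoint #2 as "Acute device success, defined as AVG flow at the end of the procedure as determined by palpable graft thrill and/or audible bruit", followed by "without significant bleeding or emergent surgery". Endpoint #6 in the same section explains one of those terms: "significant bleeding (defined as bleeding requiring treatment". Emergent surgery is not defined.

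Section 10.0 deals with the failed attempt in a NOTE under General Procedure. The NOTE applies "if connection of the venous graft segment using the VIG is attempted but not able to be completed". The surgeon then sutures the venous end, and the NOTE adds: "Such situations will be considered as an acute device failure".

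Three other places bear on the point:

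- Section 10.0, on device failures and defects: "If use of the VIG is attempted but ultimately the device is not able to be used, a Device Malfunction CRF should be submitted".
- Section 10.0, Bailout Procedure, on a VIG that does not deploy or seal properly, among other examples: "In such cases, the subject should be referred for surgical intervention".
- Section 18.0: eligible subjects with an attempted VIG use form the intention-to-treat population. No hypothesis is tested, any confidence intervals are nominal and not meant for labeling, and a full data listing is produced.

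**The concern.** Endpoint #2 is the only endpoint named as a success of the device, yet none of its three conditions mentions the device. The flow condition cannot stand in for the missing one. On checking flow at the end of the procedure, Section 10.0 says: "Thus, the AVG flow assessment is similar that used for standard sutured AVGs". A well-made sutured anastomosis can produce a thrill or bruit just as a VIG connection can.

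A subject converted to suture, with flow and without significant bleeding or emergent surgery, therefore meets every condition written in Section 8.0. The NOTE calls the same subject a failure. Neither section cites the other. The Section 8.0 reading favours the device, and with so few subjects a single case visibly moves the percentage.

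**Working it through.** The plan states no target, power or expected rate for Endpoint #2, so there is no figure to reproduce. The check is a comparison of the rules, followed by the size of the error if one rule were missed.

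**Step 1. Score the possible cases.**

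| Case | Section 8.0 alone | Section 10.0 NOTE | Both together |
|---|---|---|---|
| VIG connection made; flow; no significant bleeding or emergent surgery | Success | Silent | Success |
| VIG connection made; no flow, or significant bleeding, or emergent surgery | Failure | Silent | Failure |
| Converted to suture; no flow, or significant bleeding, or emergent surgery | Failure | Failure | Failure |
| Converted to suture; flow; no significant bleeding or emergent surgery | Success | Failure | Failure |

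Only the last row differs. The NOTE is a specific rule for that event, while Section 8.0 is a general definition. Acute device failure is the complement of acute device success, and no other endpoint uses that wording. The only coherent reading is that the NOTE completes Endpoint #2. For conversions, the missing definition of emergent surgery does not matter, because both conversion rows end in failure.

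**Step 2. Check the denominator.** Section 18.0 includes a subject once VIG use has been attempted, so a conversion cannot drop out of the rate.

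**Step 3. Check the data.** Section 10.0 requires a Device Malfunction CRF for an attempted but unusable VIG, with malfunctions reported within 24 hours of discovery. The case can be identified without new data collection.

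**Step 4. Size if the NOTE were overlooked.** Take N = 15 (the maximum in Section 6.0), one conversion of the last-row type, and all other subjects successful. Intervals are exact (Clopper-Pearson) two-sided 95%.

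- Section 8.0 alone: 15/15 = 100%. Lower limit 0.025^(1/15) = 0.782, so 78.2–100%.
- With the NOTE: 14/15 = 93.3%, interval 68.1–99.8%.
- Difference: 1/15 = 6.7 points per conversion.

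**Step 5. How often it could arise.** The documents give no conversion rate for the pivotal study. The first-in-human study had 9/9 deployment success, so 0/9 failures, with upper limit 1 − 0.025^(1/9) = 33.6%. That excludes little, so the conversion rate p has to be assumed. The chance of any conversion in 15 attempts is 1 − (1 − p)^15:

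| Assumed p | 1% | 2% | 5% | 10% |
|---|---|---|---|---|
| Chance of at least one | 14.0% | 26.1% | 53.7% | 79.4% |

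These are upper limits on the chance of a disputed case, since only a share f of conversions would meet all three Section 8.0 conditions. At f = 0.5 the chances, from 1 − (1 − pf)^15, fall to 7.2%, 14.0%, 31.6% and 53.7%. At f = 0 they are zero. The expected error in the rate is p × f × q, where q is the probability that the analyst ignores the NOTE. Even p = 10% and f = 1 give an error only in proportion to q: 10 points at q = 1 and 0 at q = 0.

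**The case for a change.** The best case for a change is about how programs get written. An analyst works from the endpoint definitions, and the NOTE sits in a procedural section without naming Endpoint #2. Section 24.0 relies on objective endpoint criteria as a protection against bias, and a definition that needs a second section to be complete is weaker than it should be. If a conversion occurred and the rule were debated only then, the choice would be made with the result in view. The phrase stating that conversion is not expected gives little comfort, since the sponsor still wrote a rule for it.

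What stands is that the Section 8.0 sentence is incomplete and has no pointer to the NOTE. The rest carries less weight. The rule is already fixed in the protocol before any conversion, so there is no choice left to make afterwards. Ignoring it would mean reporting as a device success a subject whom the protocol calls a device failure and for whom a malfunction form exists. The full listing would let a reader see that case.

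Some things cannot be checked. The CRF and the Instructions for Use were not available for this review and may carry the rule too. Section 6.0 says the endpoints match the VIG-only study, but the documents do not say how that study counted conversions.

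**Conclusion.** No change follows. Section 8.0, the Section 10.0 NOTE and the Section 18.0 population together give one answer for every conversion: failure, counted in the denominator. Added wording in Endpoint #2 would restate a rule the protocol already contains, and a new denominator sentence would repeat Section 18.0. A cross-reference would help the reader but would alter no reported figure.

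The effect is zero if the NOTE is applied. If it were missed, the effect is 6.7 points per qualifying conversion at N = 15, in a descriptive summary with no hypothesis test and no labeling use. This rests on two assumptions: that the analyst reads the NOTE as part of the endpoint, which its wording supports, and that conversions are recorded as Section 10.0 requires. The conversion rates used for scale are assumed, not taken from the documents.
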